**Table xx      Quality of life**

Outcome	Active arm (n=)	Placebo arm (n=)	Overall (n=)	P-value
FACT-G subscale score at study day 12				
Physical well-being - mean (SD)				
Social/family well-being - mean (SD)				
Emotional well-being - mean (SD)				
Functional well-being - mean (SD)				

## Statistical Analysis Plan

FACT-G total score at study day 12 - mean (SD)				
FACT-Th total score at study day 12 - mean (SD)				
FACT-G subscale score at study day 30				
Physical well-being - mean (SD)				
Social/family well-being - mean (SD)				
Emotional well-being - mean (SD)				
Functional well-being - mean (SD)				
FACT-G total score at study day 30 - mean (SD)				
FACT-Th total score at study day 30 - mean (SD)				
All quality of life outcome analyses are adjusted for centre.				

**Table xx      Safety outcomes table**

Outcome	Active arm (n=)	Placebo arm (n=)	Overall (n=)	P value
All-cause mortality during the first 30 days after the first dose of trial treatment is administered – % (95% CI)				
Hazard ratio (95% CI)				
All-cause mortality during the first 120 days after the first dose of trial treatment is administered – % (95% CI)				
Hazard ratio (95% CI)				
Number of thrombotic events from first administration of trial treatment up to and including 120 days after the first dose of trial treatment is received, per day at risk (N)				
Number of participants developing Veno-occlusive Disease within 60 days of first administration of trial treatment (N)				
Death due to thrombosis during the first 120 days after the first dose of trial treatment is administered – % (95% CI)				
Hazard ratio (95% CI)				
Death due to bleeding during the first 30 days after the first administration of trial treatment is received – % (95% CI)				
Hazard ratio (95% CI)				

**Table xx      Safety data summary - data are numbers**

## Statistical Analysis Plan

Outcome	Active arm (n=)	Placebo arm (n=)	Overall (n=)
Total number of serious adverse events (SAE) up to day 60			
Sepsis			
Organ failure			
GvHD			
Transfusion reaction			
Fever			
Other SAEs			
Number of participants experiencing at least one SAE			
Symptomatic thrombotic events up to day 120			
Venous thromboembolisms			
Arterial ischaemic events			
Veno-occlusive disease up to day 120			
Unexpected adverse reactions up to day 60			
Deaths up to day 120			

All SAEs, unexpected adverse reactions, thrombotic events and veno-occlusive disease are reported in full in Appendix 1.

### 5.6 Missing Data tables

**Table xx Missing secondary efficacy outcomes data table – n/N (%)**

	Active arm (n=)	Placebo arm (n=)	Overall (n=)
Missing data for platelet transfusions up to study day 30			
Missing data for red cell transfusions up to study day 30			
Missing data for FACT-G subscale score at study day 12			
Missing data for FACT-G total score at study day 12			
Missing data for FACT-Th total score at study day 12			
Missing data for FACT-G subscale score at study day 30			
Missing data for FACT-G total score at study day 30			
Missing data for FACT-Th total score at study day 30			

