### 4.2 Analysis principles

Unless otherwise specified, all tests will be two-sided and p-values of less than 0.05 will be considered as evidence of a difference between treatment arms.

Multiple comparisons will be performed and this may increase the probability of observing a statistically significant result by chance. No adjustments will be made to account for multiple testing.

P-values will be reported to four decimal places with p-values less than 0.00005 as <0.0001. SAS or R will be used to conduct analyses.

All analyses will be adjusted for the stratification variable (recruitment site). Recruitment site will be accounted for by including a random effect in each model.

All hazard, odds and rate ratios will be presented as active treatment versus placebo. A ratio which is greater than 1 indicates that the hazard, odds or rate is greater in the active treatment arm. 95% confidence intervals will be presented with all ratios. P-values for regression models will be obtained by comparing  $-2 \times \log\text{-likelihood}$  values for models with and without the treatment term.

The key demographics and clinical condition of the participants at consent will be presented for each arm of the trial to describe the cohort. A CONSORT diagram will be presented to show how participants progressed through the trial.

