## Statistical Analysis Plan

---

unadjusted median, IQR number of red cell transfusions per day in hospital will be reported.

- Proportion of participants surviving up to 30 days without a platelet transfusion will be estimated by the Kaplan-Meier method and compared by treatment arm using Cox regression analysis. The event of interest is time to first platelet transfusion or death. Participants withdrawn or lost to follow up before day 30 will be censored at the time that they withdrew/were lost to follow up.
- Proportion of participants surviving up to 30 days without a red cell transfusion will be estimated by the Kaplan-Meier method and compared by treatment arm using Cox regression analysis. The event of interest is time to first red cell transfusion or death. Participants withdrawn or lost to follow up before day 30 will be censored at the time that they withdrew/were lost to follow up.
- Quality of life at study days 12 and 30 will be assessed using FACT-G and FACT-Th health questionnaires. For the FACT-G subscale scores (physical well-being, social/family well-being, emotional well-being, functional well-being), FACT-G total score and FACT-Th total score, mean (SD) will be calculated and compared by treatment arm using normal regression analysis. For each normal linear regression model, residual plots will be examined. If there is substantial evidence of skew or non-constant variance, log-transformed values will be used instead.

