### 4.8 Procedures for handling Missing Data

For all outcomes, the volume of missing data will be summarised by treatment arm.

Participants withdrawn or lost to follow up before day 30 will be included in the primary outcome analysis (and in secondary outcome analyses where possible), censoring at the time that they withdrew/were lost to follow up.

It is expected that deaths and other safety outcomes, other than for participants withdrawn or lost to follow up, will be fully reported.

For the main analysis of the primary outcome, any missing bleeding assessments during the 30-day follow up period or to the last point of contact, whichever is first, will be assumed to be grade 1 or below. Sensitivity of the primary outcome to missing data will be assessed as per the sensitivity analysis described above.

Missing values for secondary and baseline characteristics will not be imputed. Missing data will be excluded from the relevant analyses.

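### The quality-of-life comparison at day 30 leaves out the day 12 scores of participants with no day 30 score; one repeated-measures model per score would use them at almost no cost

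*SAP*

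**What the plan says.** SAP 4.4 sets the schedule and the method. "Quality of life at study days 12 and 30 will be assessed using FACT-G and FACT-Th health questionnaires", and for the four FACT-G subscales, the FACT-G total and the FACT-Th total, "mean (SD) will be calculated and compared by treatment arm using normal regression analysis". That these are separate fits per score and visit is not stated in so many words, but it is the natural reading. The text speaks of several models ("For each normal linear regression model, residual plots will be examined"), and the quality-of-life table in SAP 5.5 has separate rows for day 12 and day 30 under a P-value column.

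The only adjustment named is for site. SAP 4.2 says "Recruitment site will be accounted for by including a random effect in each model", and the footnote to the quality-of-life table says "All quality of life outcome analyses are adjusted for centre". A random participant effect is specified in SAP 4.4 and 4.5 for daily bleeding, thrombocytopenia and fever, but not for FACT.

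SAP 4.8 gives the rule for gaps: "Missing values for secondary and baseline characteristics will not be imputed. Missing data will be excluded from the relevant analyses". The multiple imputation in SAP 4.7 covers bleeding assessments for the primary outcome only. SAP 5.6 counts missing FACT data by arm and visit, including "Missing data for FACT-Th total score at study day 30". Protocol 11.5.1 gives no method for quality of life, so it does not alter this.

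**The concern.** A participant who answered on day 12 but not on day 30 contributes nothing to the day 30 comparison. Yet the two scores come from the same person 18 days apart and are likely to be correlated, so the day 12 score says something about the missing one.

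Two things are at stake. The first is precision, which is lost whatever the pattern of non-response. The second is bias. In people having intensive chemotherapy or transplantation, those who feel worse may be less likely to return a questionnaire. If that selection is stronger or more frequent in one arm, the day 30 respondents are no longer comparable, and a difference can appear when treatment has none. Quality of life is a listed secondary efficacy outcome, and SAP 4.2 treats p below 0.05 as evidence of a difference.

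**Working it through.** The plan states no FACT standard deviation, effect size, power or response rate, so there is no figure of its own to reproduce. The calculation below shows what the planned method does under stated assumptions.

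**Inputs**
- From the documents: two-sided 5% test (SAP 4.2); required sample size 586 (SAP 1.5.2), hence 586/2 = 293 per arm.
- Assumed: scores with SD 1 at each visit and correlation ρ of 0.6 or 0.7; no true treatment effect; 85% response at day 12; 58% response at day 30 in one arm and 66% in the other. The log-odds of responding at day 30 rise by 0.7 or 1.0 per SD of the day 12 score.

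**Precision**

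When day 30 responders are a subset of day 12 responders, the variance of the joint estimate relative to complete cases is approximately 1 − ρ²(1 − n30/n12).
- ρ = 0.7, response falling from 85% to 80%: 1 − 0.49 × (1 − 0.80/0.85) = 0.97, a 3% reduction.
- ρ = 0.7, falling from 85% to 64%: 1 − 0.49 × (1 − 0.64/0.85) = 0.88, a 12% reduction.
- At 62%, the average of 58% and 66%: 0.90 for ρ = 0.6 and 0.87 for ρ = 0.7, reductions of 10% and 13%.

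**Bias when response depends on the day 12 score**

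The mean day 30 score among responders is ρ times their mean day 12 score. The bias is therefore ρ × (responder mean in the 58% arm − responder mean in the 66% arm). Integrating the logistic response curve over a standard normal score gives these responder means at day 12:

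| Log-odds per SD | 58% respond | 66% respond |
|---|---|---|
| 0.7 | 0.2652 | 0.2160 |
| 1.0 | 0.3482 | 0.2845 |

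With unit SD the standard error is √(1/(293 × 0.58) + 1/(293 × 0.66)) = 0.105. Selection narrows the spread among responders slightly, giving 0.101 to 0.103, which is used here. The false-positive rate is 1 − Φ(1.96 − |b|/SE) + Φ(−1.96 − |b|/SE), where b is the bias.

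| Log-odds per SD, 58% arm / 66% arm | ρ | Bias (SD) | False-positive rate |
|---|---|---|---|
| 0.7 / 0.7 | 0.6 | 0.6 × 0.0492 = 0.030 | 5.9% |
| 0.7 / 0.7 | 0.7 | 0.7 × 0.0492 = 0.034 | 6.3% |
| 1.0 / 1.0 | 0.6 | 0.6 × 0.0637 = 0.038 | 6.6% |
| 1.0 / 1.0 | 0.7 | 0.7 × 0.0637 = 0.045 | 7.3% |
| 1.0 / 0.7 | 0.6 | 0.6 × 0.1322 = 0.079 | 12.1% |
| 1.0 / 0.7 | 0.7 | 0.7 × 0.1322 = 0.093 | 14.9% |
| 0.7 / 1.0 | 0.6 | 0.6 × (−0.0193) = −0.012 | 5.1% |
| 0.7 / 1.0 | 0.7 | 0.7 × (−0.0193) = −0.014 | 5.2% |

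A positive bias favours the arm with fewer responders, if higher scores mean better health. With the same rate and mechanism in both arms the two responder means are equal and the bias is zero. In simulation, the estimate that also uses the day 12 scores had bias of 0.00 in these settings.

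**Bias when response depends on the unseen day 30 score**

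With 58% and 66% response and equal dependence in both arms, simulation gives a complete-case bias of about 0.05 to 0.06 SD. Using the day 12 score leaves about 0.03 to 0.04 SD of it.

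**The case against.** The strongest reply is that no input to the bias calculation comes from the documents. The trial is double-blind and placebo-controlled, and participants who stop treatment stay in follow-up (protocol 8.5). Nothing in the plan suggests that questionnaire response will differ by arm; if it does not, only the precision gain remains. Separate regressions per visit are also a legitimate and simpler choice, and SAP 4.8 and 5.6 would at least show unequal response rates. All of this stands, and it is why the point is optional. Counting missing scores by arm does not correct the estimate, however. Nor would it reveal equal rates that arise from different mechanisms.

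A second reply is that the remedy suits the mechanism assumed. Someone too ill to answer on day 30 is missing because of day 30 health, and there the two-visit model helps only in part. This also stands, and the fix allows for it.

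A reader might infer more than the documents support:
- That the day 12 scores are discarded. They are not: they count in full in the day 12 comparison and are unused only at day 30.
- That the day 30 result will be biased, or that an error rate of 12% to 15% is to be expected. That range needs lower response and steeper dependence on the score in the same arm. With the slopes reversed, the error is about 5%.

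**Conclusion.** The point holds as an optional improvement. SAP 4.4 and 4.8 together give complete-case comparisons at each visit, and no other section changes that for quality of life. The loss of precision is modest: the joint model would cut the variance of the day 30 difference by about 3% to 12%, with 13% in the least favourable setting tried.

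Bias is conditional on score-related non-response differing between arms in rate or mechanism. Under the assumed 58% and 66% response, correlation 0.6 to 0.7 and equal dependence on the day 12 score, it is about 0.03 to 0.04 SD, with a false-positive rate of 6% to 7%. It reaches 0.08 to 0.09 SD and 12% to 15% only if the lower-responding arm also has the steeper dependence. These rates, slopes and correlations are illustrations and not forecasts. The primary analysis is untouched.

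**What to change.** In SAP 4.4, replace the per-visit regressions, for each FACT score, by one linear mixed model with day 12 and day 30 as repeated measures. Include arm, visit and arm-by-visit terms, an unstructured within-participant covariance and the random site effect already planned. Include every participant with at least one post-baseline score, and report the arm difference with its 95% confidence interval at each visit. Amend SAP 4.8 to say that a missing score at one visit does not remove the participant from this model.

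Add to SAP 4.7 a simple sensitivity analysis for non-response that depends on the unseen day 30 score, for example shifting the missing day 30 scores by a fixed amount separately in each arm. State how deaths before day 30 are handled; SAP 1.5.2 cites about 1% deaths in the earlier platelet trial, so few are expected.

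The cost is SAP wording and slightly more modelling, with no new data. The model assumes scores are missing at random given the observed ones, which should be stated. If response proves balanced, little is lost and some precision is gained.

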## Statistical Analysis Plan

---

### 5.7 Other Outcome summary tables

**Table xx Proportion of days with thrombocytopenia**

Outcome	Active arm (n=)	Placebo arm (n=)	Overall (n=)	P value
Proportion of days with thrombocytopenia (<math><10 \times 10^9/L</math>) from randomisation up to study day 30 - % (95% CI)				
Odds ratio (95% CI)				
Proportion of days with thrombocytopenia (<math><30 \times 10^9/L</math>) from randomisation up to study day 30 - % (95% CI)				
Odds ratio (95% CI)				
Proportion of days with thrombocytopenia (<math><50 \times 10^9/L</math>) from randomisation up to study day 30 - % (95% CI)				
Odds ratio (95% CI)				
Proportion of missing platelet counts from randomisation up to study day 30 – n/N (%)				
All analyses are adjusted for centre and participant.				

**Table xx Proportion of days with fever**

Outcome	Active arm (n=)	Placebo arm (n=)	Overall (n=)	P value
Proportion of days with fever (highest daily temperature $\geq 38.1^\circ\text{C}$ ) of days spent in hospital, up to study day 30 - % (95% CI)				
Odds ratio (95% CI)				
Missing fever data up to study day 30 – n/N (%)				
All analyses are adjusted for centre and participant.				

**Table xx Reasons for transfusions – n/N (%)**

Outcome	Active arm (n=)	Placebo arm (n=)	Overall (n=)
Reasons for platelet transfusions			
Prophylaxis for platelet count $\leq 10 \times 10^9/L$			
Prophylaxis and platelet count $> 10 \times 10^9/L$			
Invasive procedure			
Active bleeding			

## Statistical Analysis Plan

Missing data for reasons for platelet transfusions			
Reasons for red cell transfusions			
Low haemoglobin			
Active bleeding			
Other			
Missing data for reasons for red cell transfusions			

**Table xx** **Summary of trial treatment**

	Arm A (n=)	Arm B (n=)	Overall (n=)
Number of participants ever on treatment – n/N (%)			
Number of days on treatment – median (IQR)			
Number of participants ever on oral treatment – n/N (%)			
Number of days on oral treatment – median (IQR)			
Number of participants who changed route or frequency (N only)*			
From oral to IV			
From IV to oral			
Reduced frequency			
Increased frequency			
Reason for frequency change 			
Renal impairment			
Other			
Missing data for route or frequency change – n/N (%)			
Number of participants who have missed a dose in a 24 hour period – n/N (%)			
Number of participants who have discontinued treatment – n/N (%)			
>30 days since started treatment			
Spontaneous increase in platelet count			
>50 x 10  /L			
3 consecutive days with morning platelet count >30 x10  /L			
Received open label TXA, other antifibrinolytic agent or procoagulant drug			
Started anticoagulant or antiplatelet therapy			
Visible haematuria			
Diagnosis of thrombosis			
Anuric			

## Statistical Analysis Plan

Developed sinusoidal obstructive syndrome			
Clinical decision			
Unacceptable adverse reaction to trial treatment			
Change in participant's condition			
Participant's decision			
Missing data for reason for discontinuation of treatment – n/N (%)			

\* Participants may appear more than once

 Reason for frequency change not reported for 1 participant.

**Table xx      Location of bleeding – n/N (%)**

Location of bleeding	Active arm (n=)	Placebo arm (n=)	Overall (n=)
Skin			
Oropharyngeal			
Epistaxis			
Gastrointestinal			
Blood in urine			
Soft tissue and musculoskeletal			
Haemoptysis			
Invasive procedure			
Abnormal vaginal bleeding			
Retinal or vitreous			
Body cavity/other			
Subconjunctiva of the eye			

**Table xx      Other outcomes – n/N (%)**

Outcome	Active arm (n=)	Placebo arm (n=)	Overall (n=)
Number of participants on Mylotarg up to study day 30			
Missing Mylotarg data up to study day 30			
Number of granulocyte transfusions/participant up to study day 30			
Missing granulocyte transfusion data up to study day 30			
Number of participants requiring interventions and procedures for bleeding up to study day 30			
Missing data for interventions and procedures for bleeding up to study day 30			

## Statistical Analysis Plan

Number of participants requiring concomitant medication up to study day 30			
Missing data for concomitant medication up to study day 30			

### 5.8 Sub-group analysis tables

**Table xx Primary outcome - UK participants vs Australian participants** [table will only be produced if evidence of heterogeneity at the interim analysis]

	UK		Australia	
	Active arm (n=)	Placebo arm (n=)	Active arm (n=)	Placebo arm (n=)
Proportion of participants who die or have bleeding of WHO grade 2 or above from day 1 up to study day 30 - n/N (%)				
Hazard ratio (95% CI)				
P-value for interaction term				
All primary outcome analyses are adjusted for centre.				

**Table xx Primary outcome - Platelet count at consent ( $\leq 30 \times 10^9/L$  vs.  $> 30 \times 10^9/L$ )**

	$\leq 30 \times 10^9/L$		$> 30 \times 10^9/L$	
	Active arm (n=)	Placebo arm (n=)	Active arm (n=)	Placebo arm (n=)
Proportion of participants who die or have bleeding of WHO grade 2 or above from day 1 up to study day 30 - n/N (%)				
Hazard ratio (95% CI)				
P-value for interaction term				
All primary outcome analyses are adjusted for centre.				

**Table xx\_a Primary outcome - Treatment compliance during first 30 days of the trial (participant decided to stop taking trial treatment vs. participant did not decide to stop taking trial treatment)**

	Participant decided to stop trial treatment	Participant did not decide to stop trial treatment
--	--	---

## Statistical Analysis Plan

	Active arm (n=)	Placebo arm (n=)	Active arm (n=)	Placebo arm (n=)
Proportion of participants who die or have bleeding of WHO grade 2 or above from day 1 up to study day 30 - n/N (%)				
Hazard ratio (95% CI)				
P-value for interaction term				
All primary outcome analyses are adjusted for centre.				

**Table xx\_b Primary outcome - Treatment compliance during first 30 days of the trial (participant decided to stop taking trial treatment during the period of over-encapsulated oral treatment; participant decided to stop taking trial treatment during the period of oral treatment as tablets; participant did not decide to stop taking trial treatment during the period of over-encapsulated oral treatment; participant did not decide to stop taking trial treatment during the period of oral treatment as tablets)**

	Participant decided to stop trial treatment during the period of over-encapsulated oral treatment		Participant decided to stop taking trial treatment during the period of oral treatment as tablets		Participant did not decide to stop taking trial treatment during the period of over-encapsulated oral treatment		Participant did not decide to stop taking trial treatment during the period of oral treatment as tablets	
	Active arm (n=)	Placebo arm (n=)	Active arm (n=)	Placebo arm (n=)	Active arm (n=)	Placebo arm (n=)	Active arm (n=)	Placebo arm (n=)
Proportion of participants who die or have bleeding of WHO grade 2 or above from day 1 up to study day 30 - n/N (%)								
Hazard ratio (95% CI)								
P-value for interaction term								
All primary outcome analyses are adjusted for centre.								

## Statistical Analysis Plan

### 5.9 Sensitivity and missing data analysis tables

**Table xx Baseline characteristics for all randomised participants vs. all randomised participants with platelet count  $\leq 30 \times 10^9/L$  – data are number (%) for categorical variables, and mean (SD) for continuous variables**

	Randomised participants		Randomised participants with platelet count $\leq 30 \times 10^9/L$	
	Active arm (n=)	Placebo arm (n=)	Active arm (n=)	Placebo arm (n=)
Male				
Age (years)				
Ethnicity				
White				
Asian				
Black African				
Black Caribbean				
Arab/other Middle East				
ancestry				
Aboriginal				
Other				
Mixed ethnic group:				
White/Black Caribbean				
White/Black African				
White/Asian				
White/Aboriginal				
White/Other				
Other mixed ethnic group				
Height (cm)				
Weight (kg)				
Diagnosis				
AML				
ALL				
APL				
CML				
CLL				
Hodgkins Lymphoma				
Non-Hodgkins Lymphoma				
Myeloma				
MDS				
Other				
Treatment plan				
Induction chemotherapy				
Consolidation chemotherapy				
Autograft				
Allograft				
Other				
Platelet count at consent ( $\times 10^9/L$ )				

## Statistical Analysis Plan

Platelet count at randomisation ( $\times 10^9/L$ )				
Haemoglobin at consent (G/L)				
Haemoglobin at randomisation (G/L)				
FACT-G subscale score at randomisation				
Physical well-being				
Social/family well-being				
Emotional well-being				
Functional well-being				
FACT-G total score at randomisation				
FACT-Th total score at randomisation				
Medical history				
Diabetes requiring treatment				
Hypertension requiring treatment				
Renal impairment requiring treatment				
Confirmed invasive fungal infection				
Other malignancy				
HLA antibodies				

